## 7.2. Dosage and Administration

Lapatinib should be given orally on an empty stomach (either 1 hour before or 1 hour after meals) at the dose of 1500 mg per day until PD, unacceptable toxicity or death whichever occurs first.

Lapatinib therapy should NOT be taken with grapefruit, grapefruit juice and these should not be taken at anytime during the study,

If vomiting occurs after lapatinib intake, the patient should be instructed not to retake the dose. If vomiting persists, then the patient should contact the investigator.

## 7.3. Dose Adjustment, Delays and Dose Modifications

Subjects will be treated until disease progression or withdrawal from study due to unacceptable toxicity or consent withdrawal. Every 4-week period subjects will be evaluated for evidence of drug-related toxicity. Throughout the study, the following criteria will be used to evaluate toxicity in haematology, blood chemistry and any nonhematologic toxicity.

Non-Hematologic Toxicity	Any Grade 3 or 4 drug-related toxicity
Hematology	ANC is < 1.0 x 109/L
	Platelet count is < 75.0 x 109/L
Chemistry	Unresolved grade 3 or 4 toxicity (except bilirubin)
	See Section 7.3.2 for liver function test abnormalities
Serum Creatinine and Calculated	≥2.0 mg/dL
Creatinine Clearance 	≤ 25 mĽ/min

Treatment will be **delayed if**:

1. Calculated by the Cockcroft and Gault Method

Treatment may be delayed up to 2 weeks, to allow for resolution of toxicity except in the event of NCI CTCAE Grade 3 and 4 Left Ventricular Cardiac Dysfunction or NCI CTCAE Grade 3 and 4 interstitial pneumonitis, *events that require patient's withdrawal*. The investigator must consult with the Study Medical Monitor prior to continuing therapy for any subject requiring a delay of more than 2 weeks for unresolved toxicity, but in general, such subject should be withdrawn from the study.

If treatment is delayed for reasons other than toxicity (i.e. unplanned travel or vacation, or lack of transportation to the site) and the subject has insufficient investigational product available, the subject should resume the usual dosing schedule once the drug supply has been made available. However, if the subject has been off therapy for more than 2 weeks, the Investigator must consult with the Study Medical Monitor prior to continuing therapy.

Dose reduction for drug-related toxicity is permitted, however the Study Medical Monitor must be consulted prior to implementing any change in dosing. Once the dose has been reduced, subjects should not be rechallenged to a higher dose level. If a NCI CTCAE Grade 3 and 4 drug-related event (other than Left Ventricular Cardiac Dysfunction or Interstitial Pneumonitis) has occurred, the investigator may discuss with the GSK Medical Monitor whether a reduction of dose is appropriate.

Lapatinib starting dose and dose modifications for unacceptable toxicity are listed in Table 1. For toxicity that is thought to be related to lapatinib, the daily dose of lapatinib will be decreased according to the schedule displayed in the Table 2. Lapatinib dose adjustments are to be made according to the greatest degree of toxicity. Toxicities will be graded using NCI Common Terminology Criteria for Adverse Events (CTCAE) version 3.0.

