## Table 2Dose Reduction Criteria and Guidelines for Management of Iapatinib
Associated Toxicity

Toxicity	Grade	Guideline for Management	Lapatinib Dose Modification 
Diarrhea	1	stop all lactose containing products, drink 8-10 large glasses of clear liquids a day, eat frequent small meals	None
	2	Loperamide (4 mg at first onset, followed by 2 mg every 2–4 hrs until diarrhea free for 12 hrs)	Consider a dose reduction of lapatinib (discuss with medical monitor)
	≥ 3(despite optimal use of loperamide)		Hold until recovery to $\leq$ grade 1, up to 21 days  . And then reduce 1 dose level.
Rash	1 2 ≥ 3	No intervention Any of the following: minocycline  , topical tetracycline or clindamycin, topical silver sulfadiazine, diphenhydramine, oral prednisone (short course)	None None; If unacceptable to patient or medically concerning then hold until recovery to $\leq$ grade 1, up to 21 days  . Restart at same dose  . Hold until recovery to $\leq$ grade 1, up to 21 days  . And then reduce 1 dose level.
Other Toxicity (excluding left ventricular dysfunction	2	No Intervention Treatment as appropriate	None None; If unacceptable to patient or medically concerning then hold until recovery to $\leq$ grade 1, up to 21 days  . Restart at same dose  .
and pneumonitis, see below)	2 prolonged or clinically significant and grade $\geq 3$	Treatment as appropriate	Hold until recovery to < grade 1, up to 21 days and then reduce 1 dose level 

1. if no recovery after 2 weeks of holding drug, patients must be withdrawn from unless in the opinion of the investigator & GSK Medical Monitor, there is reason to believe that the patient is still experiencing clinical benefit.

2. if dose has been previously held for grade 2 toxicity and grade 2 symptoms recur, OR if the patient finds the symptoms unacceptable, hold dose until recovery to < grade 1 and then reduce dose one level

3. recommended dose: 200mg po bid (loading dose), followed by 100mg po bid for 7-10 days

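### Section 7.3 contradicts itself on the restart dose after grade 3-4 drug-related toxicity: the text leaves a reduction to discretion, Table 2 requires it

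*Protocol*

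**What the plan says.** Protocol Section 7.3 deals with drug-related toxicity in narrative text and in Tables 1 and 2.

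- **Narrative, hold.** The non-haematologic criterion for delaying treatment is "Any Grade 3 or 4 drug-related toxicity". For chemistry, only grade 3 or 4 toxicity that has not resolved triggers a delay. Liver tests are referred to Section 7.3.2.
- **Narrative, dose.** Reduction is allowed, and the Medical Monitor must be consulted before the dose is changed. After a grade 3 or 4 drug-related event, other than left ventricular dysfunction or interstitial pneumonitis, "the investigator may discuss with the GSK Medical Monitor whether a reduction of dose is appropriate". Consultation is also required "prior to continuing therapy for any subject requiring a delay of more than 2 weeks for unresolved toxicity".
- **Lead-in to the tables.** For toxicity thought to be related to lapatinib, "the daily dose of lapatinib will be decreased according to the schedule displayed in the Table 2". It adds: "Lapatinib dose adjustments are to be made according to the greatest degree of toxicity".
- **Table 1.** The starting dose is 1500 mg/day and the single listed reduction is to 1250 mg/day. A patient who needs a second reduction leaves the study by default. The narrative advises against going back up after a reduction.
- **Table 2.** For grade 3 or higher rash, and for grade 3 or higher diarrhoea "despite optimal use of loperamide", the drug is held until recovery, followed by "And then reduce 1 dose level". For other toxicity of grade 3 or higher, the hold is "up to 21 days and then reduce 1 dose level". Footnote 1 sets withdrawal, with an exception for patients still benefiting, if there is no recovery after 2 weeks.
- **Section 9.5.** For severe rash, stopping or reducing is described as something that may be needed. For grade 3 or 4 diarrhoea, lapatinib is to be held and the case discussed with the Medical Monitor.

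**The concern.** Sites dose from this section. If a reduction is compulsory, there is nothing left to discuss about whether to reduce. If it is optional, Table 2 is wrong. A site that follows either instruction departs from the other, and a monitor has no single standard by which to call a deviation.

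What is at stake is re-exposure at full dose after a severe drug-related event, against the protocol's own toxicity table and without sponsor medical review. The choice also carries forward. Only one reduced level is listed, and a second reduction takes the patient off study by default. Two patients with the same event can therefore be on different doses and be handled differently at their next toxicity.

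**Working it through.** The plan states no figure to reproduce. The check sets the texts side by side.

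**1. Do the two rules cover the same events?** Yes, to a large extent. The narrative sentence and the Table 2 row for other toxicity both exclude left ventricular dysfunction and pneumonitis. Liver events have their own rules in Section 7.3.2 and are set aside. Grade 3 diarrhoea before optimal loperamide is outside the Table 2 row, so it is not part of the conflict.

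**2. What does each rule prescribe?**

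| Event (grade 3 or higher, drug-related) | Section 7.3 narrative | Lead-in and Table 2 |
|---|---|---|
| Rash | Delay; reduction optional | Hold, then one level down |
| Diarrhoea despite optimal loperamide | Delay; reduction optional | Hold, then one level down |
| Other non-haematologic toxicity | Delay; reduction optional | Hold, then one level down |
| Chemistry (non-liver) | Delay only if unresolved; reduction optional | Hold, then one level down |

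For the first three rows both rules stop the drug and differ on the restart dose. For chemistry the hold differs as well.

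**3. Does Table 2 leave room for a full-dose restart?** No. It allows the same dose on restart for grade 2 rash and grade 2 other toxicity only. No cell for grade 3 or higher offers it, and footnote 1 deals only with failure to recover.

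**4. Does Medical Monitor contact close the gap?** Not in every case. Section 7.3 requires contact for a dose change or for a toxicity delay of more than 2 weeks. A same-dose restart within 2 weeks is neither. Example, with an assumed recovery time: a grade 3 drug-related rash is held and recovers in 10 days. The narrative allows 1500 mg/day with no contact; Table 2 gives 1250 mg/day. For grade 3 or 4 diarrhoea an unreviewed restart is less likely, because Section 9.5 asks for discussion with the Medical Monitor.

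**5. Size of the difference.** 1500 − 1250 = 250 mg/day, which is one 250 mg tablet (six against five). 250 / 1500 = 16.7%.

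**6. Which hold limit applies?** The Table 2 cells allow up to 21 days. Footnote 1 of Table 2, Table 1 and the narrative all work with 2 weeks. A correction that only pointed sites to Table 2 would carry this second mismatch with it.

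**The case against.** The best defence is that the section can be read as one rule. The narrative never states outright that a patient may restart at 1500 mg/day; it allows reduction and mentions a discussion. The next paragraph then gives the specific instruction, and the specific governs the general. The title of Table 2 also describes part of its content as guidelines.

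Part of this stands. Full-dose restart is implied by the optional wording, not expressly granted, and a careful site might well follow Table 2. But the protocol states no order of precedence, and the lead-in makes the table operative in directive terms. A discussion about whether to reduce makes sense only if not reducing is a possible outcome.

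A reader might infer more than the documents support:

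- **That the two rules always hold the drug first and part only at restart.** This is true for non-haematologic toxicity. It fails for chemistry, where the narrative delays only for unresolved toxicity.
- **That Section 9.5 backs Table 2.** For severe rash it is permissive, closer to the narrative. For grade 3 or 4 diarrhoea it asks for a hold and a discussion but orders no reduction.
- **That restarting at 1500 mg/day is shown to be harmful.** Nothing in the protocol shows that the full dose after recovery is unsafe. The 250 mg/day gap measures dose, not harm.
- **That the efficacy result is compromised.** The study is single-arm and each stratum is analysed separately against fixed response counts. This wording changes neither the rule nor its error rates.

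**Conclusion.** The contradiction is real and lies in the current operative text. For grade 3 or higher rash, other toxicity, and diarrhoea despite optimal loperamide, the narrative leaves a reduction open while Table 2 requires it. The result is that some patients can return to full dose without Medical Monitor review, one level (250 mg/day, 16.7%) above what Table 2 prescribes. How many cannot be computed, because no grade 3 or higher event rate is given for this population.

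The conclusion rests on reading the lead-in to Table 2 as binding and on recovery within 2 weeks, so that no consultation is triggered. It is a safety-conduct and dosing-consistency correction that should be made. It does not threaten the trial's conclusions.

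**What to change.** Replace the discretionary sentence in Section 7.3 with:

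> After a grade 3 or 4 drug-related event (other than events requiring withdrawal or covered by Section 7.3.2; for diarrhoea, grade 3 or higher despite optimal loperamide), the drug will be held for up to 2 weeks until recovery as defined in Table 2 and, after consultation with the Medical Monitor, restarted one dose level lower. If there is no recovery within 2 weeks, Table 2 footnote 1 applies. A patient already at 1250 mg/day follows the second-reduction rule in Table 1.

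Two consequential edits are needed. Change the 21-day limit in the Table 2 cells to 2 weeks, to match footnote 1. Have the severe-rash sentence in Section 9.5 refer to Table 2.

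The cost is one replaced sentence, the hold limit in Table 2 and one cross-reference at the next amendment, with a letter to sites. Design, sample size and analysis do not change.

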#### Table 1 Lapatinib Starting Dose and Dose Reduction Schedule

Starting dose	1500	
First dose reduction	mg/day 1250	If no recovery after 2 weeks of holding drug, patients
	mg/day	must be withdrawn from the study unless in the opinion of the investigator & GSK Medical Monitor, there is reason
		to believe that the patient is still experiencing clinical
		benefit

Patients requiring a second dose reduction should be taken off study unless in the opinion of the investigator & GSK Medical Monitor, there is reason to believe that the patient is still experiencing clinical benefit

## Table 2Dose Reduction Criteria and Guidelines for Management of Iapatinib
Associated Toxicity

Toxicity	Grade	Guideline for Management	Lapatinib Dose Modification 
Diarrhea	1	stop all lactose containing products, drink 8-10 large glasses of clear liquids a day, eat frequent small meals	None
	2	Loperamide (4 mg at first onset, followed by 2 mg every 2–4 hrs until diarrhea free for 12 hrs)	Consider a dose reduction of lapatinib (discuss with medical monitor)
	≥ 3(despite optimal use of loperamide)		Hold until recovery to $\leq$ grade 1, up to 21 days  . And then reduce 1 dose level.
Rash	1 2 ≥ 3	No intervention Any of the following: minocycline  , topical tetracycline or clindamycin, topical silver sulfadiazine, diphenhydramine, oral prednisone (short course)	None None; If unacceptable to patient or medically concerning then hold until recovery to $\leq$ grade 1, up to 21 days  . Restart at same dose  . Hold until recovery to $\leq$ grade 1, up to 21 days  . And then reduce 1 dose level.
Other Toxicity (excluding left ventricular dysfunction	2	No Intervention Treatment as appropriate	None None; If unacceptable to patient or medically concerning then hold until recovery to $\leq$ grade 1, up to 21 days  . Restart at same dose  .
and pneumonitis, see below)	2 prolonged or clinically significant and grade $\geq 3$	Treatment as appropriate	Hold until recovery to < grade 1, up to 21 days and then reduce 1 dose level 

1. if no recovery after 2 weeks of holding drug, patients must be withdrawn from unless in the opinion of the investigator & GSK Medical Monitor, there is reason to believe that the patient is still experiencing clinical benefit.

2. if dose has been previously held for grade 2 toxicity and grade 2 symptoms recur, OR if the patient finds the symptoms unacceptable, hold dose until recovery to < grade 1 and then reduce dose one level

3. recommended dose: 200mg po bid (loading dose), followed by 100mg po bid for 7-10 days

## 7.3.1. Criteria for Evaluating Asymptomatic Cardiac events

If a subject who is receiving full dose of Lapatinib experiences a  $\geq 20\%$  decrease in LVEF relative to baseline AND the LVEF is below the institution's lower limit of normal (LLN), another evaluation of LVEF must be performed 2 weeks later while still receiving study drug.

Upon completion of the first repeat evaluation of LVEF, the procedures described in Table 3, Table 4, Table 5, and Table 6 must be followed:

# Table 3Criteria for Continuing Study Drug Following First Repeat Cardiac
Evaluation Performed 2 Weeks Later While Still Receiving Study
Drug

Institution's Range	LVEF Relative Change From Baseline	Action to be Taken
below LLN	≥20%	temporarily withdraw study drug repeat cardiac evaluation in 2 wks and follow procedures in Table 4
below LLN	<20%	reduce to 5 tablets (equivalent to 1250mg QD active drug) repeat cardiac evaluation in 2 wks & follow procedures in Table 5
WNL	≥20%	continue study drug repeat cardiac evaluation in 2 wks and follow procedures in Table 6
WNL	<20%	continue study drug continue cardiac evaluation every 2 months; refer to Time & Events Table 8.

Abbreviations: LLN = lower limit of normal; LVEF = left ventricular ejection fraction; WNL = within normal limits

# Table 4Criteria for Continuing Study Drug Following Second Repeat
Cardiac Evaluation in Patients with LVEF below LLN and ≥20%
Relative Change from Baseline

Institution's Range	LVEF Relative Change From Baseline	Action to be Taken
below LLN	≥20%	permanently withdraw study drug repeat cardiac evaluation every 4 wks for at least 16 wks or until resolution
below LLN	<20%	permanently withdraw study drug repeat cardiac evaluation every 4 wks for at least 16 wks or until resolution
WNL	≥20%	permanently withdraw study drug repeat cardiac evaluation every 4 wks for at least 16 wks or until resolution
WNL	<20%	reduce to 5 tablets (equivalent to 1250mg QD active drug) continue cardiac evaluation every 3 months; refer to Time & Events Table 8.

Abbreviations: LLN = lower limit of normal; LVEF = left ventricular ejection fraction; WNL = within normal limits

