# Table 5 Criteria for Continuing Study Drug Following Second Repeat Cardiac Evaluation in Patients with LVEF below LLN and <20%	Relative Change from Baseline

Institution's Range	LVEF Relative Change From Baseline	Action to be Taken
below LLN	≥20%	permanently withdraw study drug repeat cardiac evaluation every 4 wks for at least 16 wks or until resolution
below LLN	<20%	permanently withdraw study drug repeat cardiac evaluation every 4 wks for at least 16 wks or until resolution
WNL	≥20%	permanently withdraw study drug repeat cardiac evaluation every 4 wks for at least 16 wks or until resolution
WNL	<20%	continue at reduced dose (1250mg OD) continue cardiac evaluation every 2 months; refer to Time & Events Table 8

Abbreviations: LLN = lower limit of normal; LVEF = left ventricular ejection fraction; WNL = within normal limits

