# Table 6Criteria for Continuing Study Drug Following Second Repeat
Cardiac Evaluation in Patients with LVEF WNL and ≥20% Relative
Change from Baseline

Institution's Range	LVEF Relative Change From Baseline	Action to be Taken
below LLN	≥20%	permanently withdraw study drug repeat cardiac evaluation every 4 wks for at least 16 wks or until resolution
below LLN	<20%	permanently withdraw study drug repeat cardiac evaluation every 4 wks for at least 16 wks or until resolution
WNL	≥20%	Reduce to 5 tablets (equivalent to 1250mg OD active drug) continue cardiac evaluation every 2 months; refer to Time & Events Table 8.
WNL	<20%	continue study drug continue cardiac evaluation every 3 months; refer to Time & Events Table 8.

Abbreviations: LLN = lower limit of normal; LVEF = left ventricular ejection fraction; WNL = within normal limits

**NOTE:** If **following a dose reduction**, a subject experiences a  $\ge 20\%$  decrease in LVEF relative to baseline **OR** the LVEF is below the institution's LLN, the subject will be permanently withdrawn from study drug and cardiac evaluations must be performed every 4 weeks for at least 16 weeks or until resolution.

 $A \ge 20\%$  relative decrease from baseline in LVEF (asymptomatic or symptomatic), that is below the institution's LLN is considered an SAE and must be reported to GSK (refer to Section 9 for definition of an SAE).

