## 8.4.7. 12 Lead Electrocardiogram and ECHO or MUGA

12-lead ECG will be obtained for at Screening and on Day 1, every 2 Cycles (8 weeks) until discontinuation of study treatment or as clinically needed. Prior to each ECG test, the subject should be at rest for approximately 10 minutes. The subject should be in the semi-recumbent or supine position; the same position must be used for all subsequent ECG tests.

ECHO or MUGA will be obtained for at Screening and on Day 1, every 2 Cycles (8 weeks) until discontinuation of study treatment or as clinically needed. The same method must be used throughout the study.

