#### Treatment modification in case of cardiac dysfunction or interstitial pneumonitis

Subjects who have a  $\geq 20\%$  decrease in left ventricular cardiac ejection fraction relative to baseline, and the ejection fraction is below the institution's lower limit of normal, should have a repeat evaluation of ejection fraction 1-2 weeks later while still receiving Lapatinib. If the repeat ejection fraction evaluation confirms a  $\geq 20\%$  decrease in left ventricular cardiac ejection fraction, and the ejection fraction is below the institution's lower limit of normal, then treatment should be temporarily discontinued. If the left

ventricular ejection fraction recovers during the next 3 weeks, after consultation with GSK, the subject may be restarted on treatment. In such a case, Lapatinib dose-reduction is indicated. For such subjects, monitoring of left ventricular ejection fraction will then be performed 2 weeks and 4 weeks after re-challenge, and then every 4 weeks thereafter. If repeat ejection fraction evaluation still shows a decrease of  $\geq 20\%$  in left ventricular ejection fraction relative to baseline, and the value is below the institution's lower limit of normal, then the subject should be withdrawn from treatment.

Subjects with an NCI CTC AE Grade 3 or 4 left ventricular systolic dysfunction or interstitial pneumonitis must be withdrawn from treatment.

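### Tables 4 and 6 set LVEF checks every 3 months while citing an 8-week schedule, and Section 9.2 gives the same restarted patient a third schedule with narrower withdrawal wording

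*Protocol*

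**What the plan says.** Section 7.3.1 starts from a fall in LVEF of at least 20% relative to baseline that is also below the institution's lower limit of normal (LLN). LVEF is repeated 2 weeks later on drug, and Tables 3 to 6 then decide what happens. Sections 7.3.1 and 8.4.5 both make these steps mandatory.

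- **Table 3**, fall not confirmed (within normal limits, change under 20%): "continue study drug continue cardiac evaluation every 2 months; refer to Time & Events Table 8". If the fall is confirmed on both criteria, the drug is held, LVEF is repeated in 2 weeks, and Table 4 applies.
- **Table 4**, recovered on both criteria at the end of the hold: "reduce to 5 tablets (equivalent to 1250mg QD active drug) continue cardiac evaluation every 3 months; refer to Time & Events Table 8". The other three rows withdraw the drug permanently.
- **Table 5**, milder pathway at the same reduced dose: "continue at reduced dose (1250mg OD) continue cardiac evaluation every 2 months".
- **Table 6**, within normal limits and change under 20%, at full dose: "continue study drug continue cardiac evaluation every 3 months; refer to Time & Events Table 8". The reduced-dose row of the same table says 2 months.
- **Note after Table 6**: after a dose reduction, either criterion alone leads to permanent withdrawal. A fall meeting both criteria is an SAE.

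Table 8 marks ECHO/MUGA during treatment in the 8-week column and not in the 12-week column. Section 8.4.7 agrees: "ECHO or MUGA will be obtained for at Screening and on Day 1, every 2 Cycles (8 weeks", until treatment stops or as clinically needed.

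The cardiac paragraph in Section 9.2 has the same trigger. It permits restart at a reduced dose, after consulting the sponsor, if the "ventricular ejection fraction recovers during the next 3 weeks". LVEF is then "performed 2 weeks and 4 weeks after re-challenge, and then every 4 weeks thereafter". If a repeat still shows a fall of at least 20% "and the value is below the institution's lower limit of normal, then the subject should be withdrawn from treatment".

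**The concern.** Table 8 is cited with two different intervals, and it supports only the shorter one. The longer interval falls on the patient with the most cardiac history among those still on drug: someone with a confirmed SAE-level fall, restarted at 1250 mg. Read literally, that patient is scanned less often than one who has had no cardiac event.

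The interval matters because the note in Section 7.3.1 requires permanent withdrawal if either criterion returns after dose reduction. An asymptomatic return is found only by a scan. Section 2.2 reports that 32 of the 38 subjects with decreased LVEF had no symptoms. The gap between scans therefore sets how long a patient who already meets a stopping rule could stay on drug.

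Section 9.2 adds to the difficulty. A site reading it would scan the same patient much more often, allow a longer recovery window without a definition of recovery, and find withdrawal named for fewer results.

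**Working it through.** **1. Do the intervals agree with Table 8?** Months to weeks: months × 365.25 / 12 / 7.

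- 2 months = 8.7 weeks, which matches 8 weeks to rounding.
- 3 months = 13.0 weeks, which is 13.0 / 8 = 1.63 times the Table 8 interval.
- Taken as three 4-week cycles, 3 months = 12 weeks. The protocol supports this looser reading: Section 8.3.1 sets tumour assessment every 12 weeks, and Section 8.6 lists CT at 3, 6, 9 and 12 months. It is still 1.5 times 8 weeks.

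Neither reading of 3 months fits Table 8.

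**2. Which reduced-dose row has the longest interval?** Table 3 (below LLN, change under 20%): 2 weeks. Table 5: 2 months. Table 6 (within normal limits, change at least 20%): 2 months. Table 4: 3 months, the longest. The 3-month row of Table 6 is at full dose and is not in this comparison.

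**3. Checks in the first 24 weeks after restart**

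| Source | Check weeks | Checks | Longest gap |
|---|---|---|---|
| Table 4, 3 months = 13 weeks | 13 | 1 | 13 weeks |
| Table 4, 3 months = 12 weeks | 12, 24 | 2 | 12 weeks |
| Table 8 | 8, 16, 24 | 3 | 8 weeks |
| Section 9.2 | 2, 4, 8, 12, 16, 20, 24 | 7 | 4 weeks |

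The literal shortfall against Table 8 is one or two scans. The count depends on the window: over 26 weeks the 13-week reading gives 2, with 3 under Table 8 and 7 under Section 9.2.

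**4. Withdrawal rules.** LVEF range (below LLN or normal) and change (at least or under 20%) give four combinations.

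| Result | Table 4 and the note | Section 9.2 |
|---|---|---|
| Below LLN, at least 20% | withdraw | withdraw |
| Below LLN, under 20% | withdraw | not stated |
| Normal, at least 20% | withdraw | not stated |
| Normal, under 20% | continue at reduced dose | restart possible if recovered (undefined) |

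Section 9.2 names 1 of the 3 results on which Section 7.3.1 withdraws. Table 3 re-checks 2 weeks into the hold; Section 9.2 allows 3 weeks.

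**5. How many patients?** Section 2.2 gives LVEF decreases in 1.3% to 1.6% of patients. Of 33 events with a recorded outcome entry (10 + 8 + 12 + 3), 10 resolved or improved on stopping; leaving out the 3 unknown gives 10/30. The protocol does not give the share reaching the Table 4 restart cell, so I assume this proportion as a proxy.

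- Any decrease, maximum of 62 subjects: 62 × 0.016 = 0.99 expected. This is a ceiling.
- Restarted patients: 62 × 0.016 × 10/33 = 0.30 expected. Probability of at least one: 1 − (1 − 0.00485)^62 = 0.26.
- Range: 62 × 0.013 × 10/33 = 0.24 to 62 × 0.016 × 10/30 = 0.33.
- If both strata stop at 16 subjects: 32 × 0.00485 = 0.16 expected.

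The proxy is generous. The restart cell needs a fall confirmed on both criteria and then recovery on both about 2 weeks into the hold, while Section 2.2 reports a median event duration of about 13 weeks. The true figure is probably below 0.3.

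**The case against.** The best defence is that this is a slip in two cells which other text already limits. Both cells point to Table 8, and Table 8 with Sections 8.4.5 and 8.4.7 keeps every treated patient on 8-weekly checks, or more if clinically needed, with no exemption after restart. The amended text listed for Amendment 03 gives 2 months for both cells. That difference is not counted as an error here, but it suggests what was intended. Section 9.5 refers cardiac function to Section 7.3.1, and Section 9.2 keeps mandatory withdrawal for Grade 3 or 4 dysfunction.

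Most of this stands as a limit on size. It does not remove the conflict: Section 7.3.1 is mandatory and contains the 3-month cells. If Table 8 governs, the cells are wrong; if the cells govern, monitoring is relaxed after an SAE.

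Three stronger readings are tempting and are not supported:

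- *That lighter monitoring was chosen for the sicker patient.* Nothing argues for it, and the reference to Table 8 points the other way.
- *That Section 9.2 keeps on drug patients whom Section 7.3.1 withdraws.* It is silent on two results and does not direct continuation. It is weaker wording, not a contrary rule, and its monitoring is the closest of the three.
- *That the patient gets one check where three are due.* This holds only if 3 months means 13 weeks and the window is 24 weeks.

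**Conclusion.** The inconsistency is certain on the current body text and should be corrected. Two cells of a mandatory cardiac algorithm state an interval about one and a half times that of the schedule they cite, and Section 9.2 gives the restarted patient a different schedule, recovery window and withdrawal wording.

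The consequence is small in number and confined to safety. The expected count rests on three assumptions: the lapatinib programme rates in Section 2.2 apply here, events that resolved or improved on stopping stand in for patients reaching the restart cell, and accrual reaches 62. The full-dose patients in Table 6 are not in that count. The response-rate design, decision rules and analysis populations are untouched. A reader might also fold in the Table 2 hold limit or the vomited-dose wording; neither concerns LVEF, and neither is part of this point.

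**What to change.** 1. In the rows for normal LVEF with a change under 20% in Tables 4 and 6, replace the 3-month interval with every 2 months (8 weeks). This is the minimum that removes the conflict with Table 8.
2. State that Section 7.3.1 is the single LVEF algorithm, with its either-criterion withdrawal rule at the end of the hold (Table 4) and after dose reduction (the note). Section 9.5 already implies this.
3. Replace the LVEF paragraph in Section 9.2 with a cross-reference to Section 7.3.1. This also removes the 3-week window and the undefined recovery. Keep the Grade 3 or 4 withdrawal sentence.
4. Optionally, so that step 3 does not loosen follow-up after re-challenge, move the Section 9.2 schedule (weeks 2 and 4, then every 4 weeks) into the Table 4 restart cell. This goes beyond what the Table 8 conflict requires.

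**Cost.** Steps 1 to 3 are amendment wording and add no scans beyond Table 8. Step 4 adds 7 − 3 = 4 scans per restarted patient in 24 weeks, or about 4 × 0.30 = 1.2 expected scans across 62 subjects. Sample size and analysis do not change.
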